**Extending long-term outcomes through an adaptive aftercare intervention**

**NCT02143063**

**Protocol**

**IRB Approval Version: 3/31/2020**

## Protocol: Extending long-term outcomes through an adaptive aftercare intervention

Principal Investigator: [name].

Reinforcement interventions have pronounced effects on reducing cocaine use. We developed and evaluated a low-cost reinforcement intervention, systematically moving it through the Stages of development to dissemination and broad clinical implementation. In an ongoing project, reinforcement interventions are yielding benefits when reinforcers are provided at treatment initiation and for longer durations. However, less than half of patients remain engaged for 12 weeks with traditional reinforcement interventions, which require frequent attendance for monitoring and reinforcing abstinence. Interventions that extend into aftercare and that are acceptable to and efficacious in preventing long-term relapse are critically needed.

Reinforcement interventions are efficacious during periods they are in effect, and pilot data show that variable interval (VI) reinforcement schedules, once behavior change occurs, hold potential for maintaining gains when administered infrequently. Assessing methods to extend benefits of these interventions is of paramount scientific and clinical concern. This study will evaluate a novel approach in which reinforcement frequency varies by patient performance. In this intervention, reinforcement will be available for 24 weeks, on a progressive VI schedule, that adapts according to patient status. Patients who maintain abstinence earn maximum reinforcers as infrequently as every three weeks on average, while frequency of monitoring and reinforcing abstinence will increase in those who relapse until abstinence is re-instated.

To test efficacy, 280 patients with cocaine use disorder will be randomly assigned to: standard care (SC), SC+traditional twice weekly reinforcement, or SC+adaptive VI reinforcement. Evaluations will be completed at baseline and throughout 18 months to assess objective and self-reported indices of drug use, psychosocial problems, and HIV risk behaviors. Primary hypotheses are (1) the adaptive VI reinforcement intervention will improve outcomes relative to standard care during the treatment period and throughout follow-up, and (2) the adaptive VI reinforcement intervention will improve outcomes relative to the traditional reinforcement system. This study will also evaluate the roles of cognitive control and treatment outcome. Patients with better cognitive control are expected to maintain longer durations of abstinence across conditions. If these measures differentially relate to outcomes across treatments, such results suggest the potential of pairing reinforcement interventions to individuals most likely to benefit from them; they may also indicate possible markers of response in a treatment-specific manner. If cognitive indices mediate treatment response, future studies can refine interventions to improve cognitive processes and long-term outcomes.

### Specific aims

Designed and tested using the NIH Stage Model of psychotherapy development (Onken et al., in press), reinforcement interventions hold great potential to improve drug abuse treatment outcomes. Community clinics are increasingly applying these interventions, but methods to maintain their benefits long-term are needed. Extending **the effects of reinforcement interventions would be a major step forward in increasing the efficacy and acceptability of this approach.** Traditional approaches toward reinforcement, requiring frequent clinic attendance, limit acceptability among both patients and providers, especially when applied over long durations. We have pilot data suggesting the efficacy of a gradually increasing variable interval (VI) reinforcement schedule in maintaining behavior gains. This study will evaluate this approach for improving short- and long-term drug use outcomes. It will also address potential cognitive mechanisms of action.

In total, 280 patients initiating treatment for cocaine use will be randomized to: standard care (SC), SC + traditional reinforcement, or SC + progressive variable interval (VI) reinforcement. The two reinforcement interventions will provide the same overall average maximum magnitudes of expected earnings. Patients in the traditional reinforcement condition will earn reinforcers twice weekly for submitting stimulant negative samples. Patients in the progressive VI reinforcement condition will earn reinforcers for providing cocaine-negative urine samples according to an increasing VI schedule; monitoring and reinforcement will occur

relatively infrequently when abstinence is maintained but increase in frequency if drug use occurs. Cell phones will maintain contact with patients in all conditions to inform them of randomly selected urine testing days throughout a 24-week period to provide, for one of the first times, objective indicators of relapse following treatment cessation. All patients will complete cognitive assessments pre, mid and post-treatment.

Primary study aims are to:

**1. Determine the efficacy of an adaptive progressive VI reinforcement intervention for reducing cocaine use in the short- and long-term.** The hypothesis is that patients assigned to the adaptive progressive VI reinforcement intervention will achieve longer periods of abstinence than patients in standard care during the period reinforcement is in effect (24 weeks). We will also evaluate how well this reinforcement intervention maintains benefits throughout follow-up (18 months).

**2. Compare the relative efficacy of adaptive progressive VI reinforcement to a traditional reinforcement intervention.** Patients receiving adaptive progressive VI reinforcement are hypothesized to achieve greater during and post-treatment abstinence than those receiving traditional twice-weekly reinforcement.

Secondary and exploratory aims of the study are to:

**a. Evaluate relations between behavioral and measures of cognitive control and response to monetary rewards and treatment outcomes.** Patients with better cognitive control are expected to achieve longer durations of abstinence, regardless of treatment assignment. Patients who are more sensitive to monetary rewards are expected to achieve longer duration of abstinence, particularly when assigned to a reinforcement intervention. We also expect that sensitivity to monetary rewards and cognitive control may increase among those who are assigned to a reinforcement intervention, and that changes in these processes may mediate drug use outcomes.

**b. Assess the impact of reinforcement interventions on HIV risk and other outcomes.** Compared to SC, reinforcement interventions are expected to reduce high risk sexual behaviors that spread infectious diseases. Reinforcement interventions are also hypothesized to decrease psychiatric symptoms and improve quality of life. Both short-term and long-term effects will be examined. Gender effects will also be explored.

**c. Estimate costs and cost-effectiveness.** We will examine costs and cost-effectiveness of interventions and estimate conditions under which, and patients for whom, these interventions may be most cost-effective.

Results from this study will be highly relevant for policy decisions as reinforcement interventions move into practice settings. If adaptive progressive VI schedules are efficacious, this would be a major advance because this approach could be applied on a long-term basis to prevent relapse. This procedure minimizes patient and provider burden relative to traditional reinforcement interventions, and *even relative to typical aftercare interventions*. Moreover, as effective as reinforcement interventions may be, little is known regarding the types of individuals who do and do not respond to them. Inclusion of cognitive measures is likely to greatly enhance our understanding of predictors of patient response, which could lead to more efficient patient-treatment matching strategies. If this project yields evidence of pre- to post-treatment changes in cognition that mediate effects of reinforcement interventions, this information has the potential to revolutionize our understanding of how these very effective interventions exert their beneficial effects.

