*a.) Cognitive control.* Deficits in cognitive control are a defining feature of addiction (Ersche et al., 2012; Goldstein & Volkow, 2011; Hyman, 2005), and the functions most commonly impaired (e.g., cognitive flexibility, inhibition, control, and attention) are the ones many treatments attempt to enhance (Sofuoglu et al., 2013). For example, learning new cognitive responses (e.g., to cravings) are critical aspects of cognitive-behavioral, motivational, and even 12-step approaches (Ersche & Sahakian, 2007; Garavan & Hester, 2007) (see Project #1). Reinforcement interventions, in contrast, rely on very basic learning principles. Such treatments have been applied for decades to individuals with severe cognitive dysfunction and mental retardation, for whom they are a standard of care (e.g., Bijou & Orlando, 1961). Because individuals with severely impaired cognitive functioning respond to reinforcement interventions, these treatments may be beneficial even among drug abusing patients with cognitive deficits, and data indicate that contingent rewards reliably and robustly sway decision making toward clinically desired behaviors (Dutra et al., 2008; Lussier et al., 2006). Nevertheless, drug using patients make choices between the alternate reinforcers provided by these interventions and the reinforcement provided by drug use. Such choices are made in patients' natural environments, where they experience cravings for drugs; when drugs become suddenly available, these choices rely on cognitive control, and the function of the prefrontal cortex (Kober et al., 2010; Volkow et al., 2010). Although cognitive control is not the primary tenet of reinforcement interventions, it may predict and contribute to treatment outcomes. Furthermore, patients practice acts of cognitive control by choosing to attend treatment and regulate craving, inhibit drug use, and maintain abstinence (DeVito et al., 2012; Muraven, 2010). Reinforcement interventions, especially if they result in continued use of these cognitive strategies while maintaining abstinence, may lead to greater cognitive control. Thus, cognitive control may be both a moderator and mediator of treatment outcomes (see prelim studies).

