We have fMRI pilot data from Carroll et al.'s (under review) trial relevant to reinforcement interventions. Pre- and post-treatment imaging data from the Stroop task (described in DeVito et al., 2012) were obtained from 22 cocaine dependent patients. Eleven were randomized to a reinforcement intervention, and 11 to a non-reinforcement intervention; all 22 received placebo medication. Two main findings emerged: 1) Greater pre-treatment Stroop activity in the dorsolateral prefrontal cortex (dlPFC) was positively correlated with reinforcers earned in those receiving the reinforcement intervention, suggesting that better cognitive-control pre-treatment may be related to better response to treatment (Fig 1). 2) Stroop activity decreased in dmPFC and dlPFC from pre- to post-treatment in those receiving the reinforcement intervention, and these effects were greater among those in the reinforcement than the non-reinforcement condition (Fig 2). We reported similar decreases in these regions in concert with improvements in Stroop performance, suggesting greater efficiency in these PFC circuits (DeVito et al., 2012) and consistent with findings noted with working memory training (Klingberg, 2010). Together, these data suggest that Stroop-related activation in the PFC may relate to outcomes, and that reinforcement interventions may be associated with changes in brain functioning in these

[figure not shown]

regions.

The Monetary Incentive Delay (MID) task is commonly used to assess neural activity during anticipation and receipt of monetary rewards (Balodis et al., 2012). Neural activity is compared between no reward (\$0) and reward conditions (\$5) during a period of anticipation, and once the outcome is revealed (winning \$5 or \$0). Compared to controls, those with drug use disorders have reduced neural response to monetary rewards in regions including the ventral striatum (VS; Andrews et al., 2011; Balodis et al., 2012; Goldstein et al., 2007). MID data are available from the 11 cocaine-dependent participants above who received a reinforcement intervention. As expected, greater pre-treatment activity in the VS during receipt of monetary rewards (outcome phase) was associated with longer abstinence during treatment (Fig 3). We also observed increases in activity in the VS pre- to post-treatment in patients receiving the reinforcement intervention (Fig 4).

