To determine if patient factors predict outcome, multiple regression analyses will be used to find predictors of continuous measures (e.g., longest duration of abstinence, percent negative samples), and logistic regressions for dichotomous dependent variables (e.g., presence or absence of stimulant use at follow-up). Cox regression analyses may also be used to determine what factors predict time to event outcomes, such as time to first positive sample after study initiation. Independent variables will include treatment condition, site, days attended groups at the clinic, drug use severity (ASI-drug scores, baseline positive samples), scores on cognitive control tasks at baseline (computer task or impulsivity scores), and demographics, including gender and race. Analyses will be conducted for the entire sample and with interactions of predictors with condition to assess if certain characteristics are more predictive of outcomes in the different treatment conditions.

Behavioral changes that result from treatment may also be a function of improving cognitive control, and reinforcement interventions may lead to reductions in drug use by enhancing cognitive functioning. If effects of reinforcement on drug use outcomes are significant, cognitive control as assessed via computer and impulsivity tasks will be evaluated as a potential mediator of effects. A latent growth model using structural equation modeling can be built. Models will be built sequentially, starting with a basic latent growth model comprising drug use days over time, modeled as slope and intercept. Important cognitive performance indices can be tested as mediators in turn. A bootstrapping resampling procedure will estimate model test statistic  $p$  values and parameter standard errors (Arbuckle, 2006). Models will be considered to fit the data if the chi-square is not significant, Comparative Fit Index (CFI) is  $>.97$ , and root mean square error of approximation (RMSEA) is  $<.10$  (Bollen & Long, 1993) using an iterative basis, with individual paths added or deleted on the basis of modification indices (Jöreskog & Sörbom, 1984). Once a basic latent growth model is determined, treatment group will be added as a predictor of slope and intercept. Then, cognitive variables (pre to post change scores) included in the model. Beta weights of the full model can be tested using a product of coefficients test to determine if mediation is significant (MacKinnon 2007a,b).

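### The exploratory mediation model enters the change in cognition without baseline cognition, which biases the cognition-to-drug-use path against the hypothesised direction, usually towards zero

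*Combined protocol and SAP*

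**What the plan says.** The mediation analysis is described near the end of Data Analysis, in the text on cognitive control as a mediator. It is built in this order:

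- The outcome side comes first, "starting with a basic latent growth model comprising drug use days over time, modeled as slope and intercept".
- The randomised arm is entered next, as an explanatory variable for both growth factors.
- The mediator follows, and only in this form: "Then, cognitive variables (pre to post change scores) included in the model".
- The last step is the significance test for the indirect effect: "Beta weights of the full model can be tested using a product of coefficients test to determine if mediation is significant".

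Baseline cognition is not a named term in this sequence. Under Data Analysis it is a model term only in the separate regressions that look for predictors of outcome, where baseline cognitive task scores are listed as independent variables.

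Elsewhere the protocol expects cognition to matter for outcome. Aim a under Specific aims says "Patients with better cognitive control are expected to achieve longer durations of abstinence, regardless of treatment assignment". Preliminary studies reports pilot imaging data "suggesting that better cognitive-control pre-treatment may be related to better response to treatment". Innovation, item 4a, concludes that "cognitive control may be both a moderator and mediator of treatment outcomes".

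**The concern.** Randomisation protects the path from treatment to cognition. It does not protect the path from cognition to drug use, where any variable related to both the mediator and the outcome is a confounder. Baseline cognition is an obvious candidate. The protocol expects it to predict outcome, and it is built into the change score with a negative sign: patients who start high tend to change less.

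The product-of-coefficients test multiplies the two paths, so bias in the second passes straight into the indirect effect. At stake is the mediation part of aim a. If the protocol's own expectations hold, a real mediator could be missed. If cognition is not a mediator, the model could suggest that improving cognition works against abstinence.

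**Working it through.** The documents give no effect size, retest correlation or power for the mediation model, so there is no figure to reproduce.

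**Inputs from the documents.** Model terms (Data Analysis); 60 patients in standard care and 110 in each reinforcement arm (Power analyses).

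**Assumptions not in the documents.** Within-arm retest correlation r = .5 to .8; equal pre and post SD; baseline-outcome slope m = .10 to .30 in SD units; treatment shift in cognition 0.46 or 0.20 SD; true mediator path b = 0, .15 or .30. The protocol's 0.46 is an effect size for post-treatment abstinence; it is only borrowed here for cognition. The outcome is scored as abstinence, so a beneficial path is positive; signs flip for drug use days.

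**1. Bias.** Let D = post − pre with unit SDs, and Y = c′T + bD + g·pre + e. Within arm, Cov(pre, D) = r − 1 and Var(D) = 2(1 − r). Omitting pre gives

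b̂ = b + g(r − 1)/[2(1 − r)] = b − g/2.

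**2. In terms of the baseline-outcome slope.** Since m = g − b(1 − r), b̂ = [b(1 + r) − m]/2. With m > 0 and b ≥ 0 this is always below b. For b > 0 the sign reverses only if m > b(1 + r).

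| b | m | b̂ at r = .5 / .7 / .8 | reversal needs m above |
|---|---|---|---|
| .30 | .10 | .175 / .205 / .220 | .45 / .51 / .54 |
| .30 | .30 | .075 / .105 / .120 | .45 / .51 / .54 |
| .15 | .30 | −.038 / −.023 / −.015 | .225 / .255 / .27 |
| 0 | .10 | −.05 throughout | no sign to reverse |
| 0 | .30 | −.15 throughout | no sign to reverse |

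**3. Unequal variances.** If the post SD is k times the pre SD, the bias is g(rk − 1)/(1 + k² − 2rk).
- k = 1.2, r = .7: −.16/.76 = −.21g.
- k = 1.2, r = .8: −.04/.52 = −.08g.
- k = 0.9, r = .7: −.37/.55 = −.67g.

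One half is therefore the equal-variance value only, and the bias runs against the hypothesis only while rk < 1.

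**4. Error rates.** Simulation, 60 v 110, r = .5 to .8, mediation declared when both paths are significant at two-sided .05. Figures move by a few points with simulation error and residual scaling.
- b = 0, m = .30, shift 0.46: wrong-direction mediation in about 24 to 41% of trials; about 2% with baseline included.
- b = 0, m = .10, shift 0.46: about 6 to 8%.
- b = 0, m = .30, shift 0.20: about 12%.
- b = .15, m = .30, shift 0.46: about 3 to 6%.
- b = .30, shift 0.46: correct detection from about 11% (m = .30) to about 50% (m = .10); 64 to 83% with baseline included.

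**5. Growth-model form.** Drug use days, r = .7, true change-to-slope path −.30. If baseline acts on the slope with −.39, the estimate is −.10 (formula: −.30 + .195). If baseline acts only on the intercept with −.30, the slope path is unbiased at −.30, but a false change-to-intercept path of +.15 appears.

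**6. Is adjustment clean?** No.
- With reliability .75 at both visits and a true path of .30, the adjusted estimate is 0.17 to 0.26 and the unadjusted one −0.01 to 0.05.
- Suppose instead that a stable trait drives the outcome, there is no mediation, and pre and post are equally noisy measures of it, each correlating .30 with the outcome. The adjusted path is then .30(1 − r)/(1 − r²) = .30/(1 + r), which is .20 at r = .5 and .17 at r = .8. The change-only path is (.30 − .30)/[2(1 − r)] = 0.

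**The case against.** The analysis is exploratory, is run only if reinforcement shows significant effects on drug use, and is loosely worded, so a baseline term is not forbidden. Paths may also be revised, "with individual paths added or deleted on the basis of modification indices". The conditional, secondary status stands and limits the importance of the point. The revision rule is no safeguard, because modification indices assess paths among variables already in the model and baseline cognition is not one of them.

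The size rests on assumptions. That also stands: the upper-end rates need a baseline-outcome correlation of .30 together with a shift of 0.46 SD, and they fall sharply when either is smaller.

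The sentence in aim a does not mention baseline. True; the pre-treatment reading comes from the pilot data and from the predictor regressions.

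A reader might go further and infer that the estimated path will come out with the wrong sign. The documents do not support that. They give neither the baseline effect nor the mediator path, and with a true path of .30 reversal needs a baseline-outcome slope above .45 to .54 for r = .5 to .8.

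Finally, adjustment brings its own risk: step 6 shows a setting in which the adjusted model creates a false path and the change-only model does not. This stands, and is why both models should be reported.

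**Conclusion.** The point holds as an analysis weakness in an exploratory aim. The model as described leaves out a variable that the protocol treats as a likely predictor of outcome and that is normally negatively correlated with the change score. If baseline cognition has a direct effect g, the mediator path is biased against the hypothesised direction, by g/2 under equal variances and by other amounts otherwise. Attenuation is the general result; a spurious or reversed path requires g to be large relative to the true path. The bias falls on whichever growth factor, intercept or slope, baseline cognition predicts.

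The omission and the direction of the bias are well supported, the latter conditional on a baseline effect. The size is illustrative: the wrong-direction and detection rates depend on a retest correlation, baseline effect and cognitive shift that the documents do not give. A reader might also infer that the trial's main conclusions are at risk. They are not: the primary comparisons of abstinence do not use this model.

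**What to change.** In the mediation text under Data Analysis, add the baseline score of the same cognitive index as a covariate of both the mediator and the growth intercept and slope, and take the indirect effect from that model. Using the follow-up score as mediator with baseline adjusted is equivalent. Keep the change-only model as a named sensitivity analysis. State that measurement error in the baseline score leaves residual confounding, which can attenuate the path or create a false one, so agreement or disagreement between the two models should be reported and interpreted.

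Cost: one covariate per model and one sensitivity analysis. Specific aims and the assessment schedule already plan a baseline cognitive assessment for all patients, so no new data are needed.

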**Data Analysis.** An important issue preceding analyses is to identify baseline differences between groups despite random assignment. Differences between groups that may be related to outcome (e.g., psychiatric diagnoses, dependence severity, clinic services received) will be used as covariates or fixed factors, as appropriate. Analysis will be conducted on an intent-to-treat basis, using all randomized patients, and both short-term (changes from baseline to month 6) and longer-term (throughout the 18-month follow-up) efficacy will be evaluated. The primary outcome is longest duration of cocaine abstinence, a continuous variable that can be transformed if needed. Groups will be compared using t-tests for normally distributed data, or ANCOVA if covariates are included. The design includes 3 treatment groups, allowing for analyses of two main effects.

Primary aim # 1 is to examine the efficacy of adaptive progressive VI reinforcement. We will compare those randomized to Group C vs Group A with respect to longest duration of abstinence during the 24-week intervention period and throughout the 18-month follow-up period.

Primary aim #2 is to assess if adaptive reinforcement improves duration of abstinence achieved relative to traditional reinforcement. We will compare those randomized to the two reinforcement conditions with respect to during treatment and long-term abstinence outcomes.

Secondary aims are to evaluate the impact of the interventions on other indices of stimulant and secondary drug use outcomes. Using the same contrasts above, we will compare groups with respect to: proportions of submitted and expected samples that test negative for stimulants and other drugs (alcohol, opioids, THC), and subjective reports of use (SUC % abstinent days). The first rely on objective indicators and such data will be available from all randomized patients. Subjective reports will supplement objective indices, and patients can be considered using if either index is positive. In terms of proportional data, missing samples will be considered missing (not impacting the denominator) in one analysis, and positive in another to consider the range of possibilities with respect to drug use outcomes. Because Group B has more expected samples (48) than the other groups ( $\geq 18$ ), proportional data for expected samples will rely upon the cell phone prompted samples ( $\geq 18$ ), designed to be similar across conditions, to conservatively test group differences.

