**Power analyses for primary aims.** Our studies reinforcing abstinence generally find Cohen's  $d$  effect sizes of 0.6 to  $> 1.0$  for during treatment drug use outcomes (Petry et al, 2000, 2002,2004,2005abc,2006a, 2007a,2010b,2011a,2012abc). In terms of post-treatment effects, our ongoing study is finding an effect size of 0.46 for a 12-week reinforcement intervention in enhancing post-treatment abstinence relative to standard care. Although we expect a larger effect size when 24 weeks of reinforcement is provided, and especially if more patients engage in the adaptive progressive VI reinforcement intervention for greater durations, we will conservatively power this study to detect a similar effect size of 0.46 between the VI reinforcement intervention and standard care for long-term outcomes. Using a Type I error rate of  $\alpha=.05$ , a Type II error rate of  $\beta=.20$ , and power=0.80 (Cohen, 1988), 60 patients/ group are needed to detect  $d=0.46$  between the standard care and reinforcement interventions (Aim 1). For Aim 2, the study is powered to detect a lower, but still clinically meaningful, effect size of 0.35 between the two active reinforcement conditions, similar to effect sizes found between reinforcement conditions in other studies (Petry et al., 2004, 2006a). Using the same power analyses outlined above, 110 patients/group are needed to detect  $d \geq .35$  between the traditional and adaptive reinforcement conditions with respect to during treatment and long-term outcomes. Thus, we will recruit 280 patients (60 in standard care and 110 each for the reinforcement interventions).

**Secondary aims** are to evaluate if reinforcement improves other indices of drug use, psychosocial functioning (ASI, BSI scores), quality of life, and HIV risk behaviors, as found in other studies (Ghitza et al., 2008; Hanson et al, 2008; Petry et al., 2007b,in press b). These are continuous measures, with missing data likely. If no systematic differences in missing data are noted (the case in our prior studies), hierarchical linear models (HLM; Gibbons et al., 1993) using MIXREG (Hedeker, 1993) will analyze differences between groups over time. These analyses have advantages over repeated measures ANOVA as they estimate missing data via model parameter

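### Mediation by cognition is listed among the aims without a condition, but the full-sample analysis runs only after a significant, undefined effect on drug use

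*Combined protocol and SAP*

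**What the plan says.** The Specific aims section says the study will address possible cognitive mechanisms and that every patient is assessed on cognition before, during and after treatment. Aim a, listed among the secondary and exploratory aims, expects reward sensitivity and cognitive control to rise under reinforcement and adds that "changes in these processes may mediate drug use outcomes". No significance condition appears there.

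The mediation paragraph under Data Analysis does set one before cognition is tested in the mediator role: "If effects of reinforcement on drug use outcomes are significant, cognitive control as assessed via computer and impulsivity tasks will be evaluated". It goes on to describe a latent growth model of days of drug use, with treatment group and then pre-to-post cognitive change added, bootstrap standard errors and a product-of-coefficients test. It does not say which group contrast, which drug use outcome, or which period has to be significant. The primary outcome elsewhere in Data Analysis is longest duration of cocaine abstinence, which is not the outcome in the mediation model.

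**The concern.** An indirect effect is tested through two paths: treatment to cognition, and cognition to drug use given treatment. Neither path needs the total treatment effect to reach .05. A condition on the total effect therefore withholds the analysis in some trials where the mediator could have been found.

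More than the indirect effect is withheld. For the full sample, change over time on the computer and impulsivity tasks appears only inside this conditional model. The predictor regressions use baseline cognitive scores. The longitudinal models under Secondary aims cover other drug use, psychosocial functioning, quality of life and HIV risk, not cognition. The fMRI analyses of change carry no condition, but they cover only the subset of 60 patients from Groups A and C. If the condition fails, the plan has no stated test across all 280 patients of whether cognition changed by arm.

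Because the condition is undefined, whether the analysis runs could also be settled after the drug use results are known.

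**Working it through.** **Inputs from the plan** (Power analyses for primary aims). Alpha is .05 and power 0.80. For Aim 1 the plan says it will "conservatively power this study to detect a similar effect size of 0.46 between the VI reinforcement intervention and standard care for long-term outcomes". For Aim 2 it uses an "effect size of 0.35 between the two active reinforcement conditions". It cites d of 0.6 to above 1.0 "for during treatment drug use outcomes". Allocation A:B:C is 60:110:110. Sidedness is not stated: "Groups will be compared using t-tests for normally distributed data, or ANCOVA if covariates are included". Two-sided is taken as the base case and one-sided shown as the range.

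**Reproducing the plan's Aim 1 figure.** With n per group = 2(z_alpha + z_beta)²/d²:
- One-sided, equal groups: 2(1.645 + 0.842)²/0.46² gives 59 per group.
- Two-sided, equal groups: 2(1.960 + 0.842)²/0.46² gives 75 per group; 60 per group has power 0.71.
- Two-sided at the actual 110:60 allocation: 58 in standard care are enough.

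The stated 60 is thus consistent with a one-sided test in equal groups, or with a two-sided test at the actual allocation. (Aim 2 at d=0.35 needs 129 per group two-sided or 101 one-sided, against the stated 110.)

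**How often the condition fails.** Noncentral t with noncentrality d × sqrt(n1 n2/(n1 + n2)):
- C v A, long-term: 0.46 × sqrt(60 × 110/170) = 2.866. Two-sided power is 0.813, so the condition fails in 18.7% of trials. One-sided: 0.887, 11.3%.
- C v A, during treatment, d=0.6: noncentrality 3.739, power 0.961, fails in 3.9%. One-sided 1.9%. At d=1.0 about 0%.
- C v B, d=0.35: 0.35 × sqrt(110 × 110/220) = 2.596, power 0.734, fails in 26.6%. One-sided 17.3%.
- Both contrasts together, with arm means A=0, B=0.46−0.35=0.11, C=0.46 (simulated, two-sided): if either suffices, it fails in about 9%; if both are required, about 36%.
- C v A significant in either period (d=0.6 during treatment, 0.46 long-term): fails in 0.7% to 3.7% for correlations between the two tests of 0 to 0.9.

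The range over readings is about 0% to 36%.

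**What is lost when it fails.** The documents give no treatment-to-cognition or cognition-to-outcome effect, so both are assumptions. The simulation uses a normal mediator and outcome, a cognition-to-outcome path of 0.30, two-sided .05 and 60 v 110 patients. The mediator counts as found when both paths are significant.

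| Total effect d (C v A) | Treatment-to-cognition | Found, no condition | Found, with condition |
|---|---|---|---|
| 0.46 | 0.46 SD | 79% | 67% |
| 0.46 | 0.30 SD | 45% | 40% |
| 0.60 | 0.46 SD | 79% | 77% |

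At d=0.46 and 0.46 SD the loss is about 12 points; at d=0.60 it is about 2.

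**The case against.** The strongest reply is that the natural meaning of a reinforcement effect is reinforcement against standard care, and that the mediator is a pre-to-post change, so the treatment period is the fitting window. The plan cites d of 0.6 or more there, and the condition would then rarely fail. That is fair, and it removes any single headline rate. A reader might infer that mediation is lost in a fifth to a quarter of trials; that holds only for one two-sided contrast at d=0.46 or 0.35, and the plan does not say that this is the condition.

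A reader might also infer a large loss for C v B. At d=0.35 and a cognition-to-outcome path of 0.30, detection would fall from about 92% to 69% if the two arms differed by 0.46 SD in cognition. Nothing supports that input: both arms are reinforced, and aim a expects cognition to improve under reinforcement generally. At 0.20 SD the fall is only from about 32% to 27%.

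Nor is aim a a firm promise. It is exploratory and hedged, and the statements in the abstract and at the end of Specific aims describe what mediation would mean if found. Upward bias in the estimates kept after the condition is small, about 4% under the 0.46 SD mediator at the plan's powering effects.

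Finally, asking for a total effect before explaining it is a recognised conservative convention, and the plan does not forbid later exploration. That stands as a defence of caution. It does not supply a contrast, outcome or window, and the baseline regressions and the fMRI subset do not replace the conditional analysis.

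**Conclusion.** The concern holds in a limited form. The aims set out cognitive mechanisms and mediation without a significance condition, while Data Analysis makes the full-sample mediation analysis depend on one that is undefined and that the chosen test does not need. At the plan's own conservative powering effect, and if the single long-term C v A test decides, the analysis is skipped in about 19% of trials two-sided or 11% one-sided. The loss in finding a mediator rests on path sizes that the documents do not give, and ranges from about 2 to 12 points in the C v A cases shown. No primary conclusion is affected. This is a cheap improvement.

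**What to change.** Delete the opening condition of the mediation paragraph. State that the indirect effect for C v A, and for C v B as a further exploratory contrast, will be estimated with bootstrap confidence intervals whatever the primary result. Report both component paths, including pre-to-post cognitive change by arm in the full sample. Label the results exploratory when the total effect is not significant.

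No new data and no change in sample size are needed. The cost is analysis time, and one more exploratory result to report and interpret cautiously if the primary comparison is null.
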